7. SAFETY ANALYSIS

7.1. General

The safety analysis set will be used for all safety analyses, unless otherwise noted. Summaries will be presented by treatment group actually received.

In this study, patients are encouraged to remain in the study and complete the remaining study assessments even after withdrawing from treatment. The assessment of safety in this context will be based on measurements and events recorded during the treatment period (on-treatment). On-treatment assessments will be defined as events and measurements occurring between the first dose of study drug and the end of treatment (week 24) visit for patients who complete treatment and between the first dose of study drug and the last dose of study drug + 4 weeks for patients who discontinued treatment early.

7.2. Study Drug Administration

The exposure to study drug will be characterized by duration of treatment and by the number of patients receiving at least 1, 2, 3, etc. injections. Total patient years will also be summarized. The summaries will be provided by treatment group and overall, and by baseline stratification factors.

Duration of treatment period is defined separately for patients who completed/discontinued treatment.

- Completed: End of treatment (week 24) visit date – first dose date + 1
- Discontinued: Last dose date – first dose date + 29

7.3. Adverse Events

Adverse events will be coded using the Medical Dictionary for Regulatory Activities (MedDRA); the final version number will be indicated in the summary tables.

On-treatment adverse event summaries will be presented by treatment group and overall, based on events with onset during the treatment period. If the AE start date is missing or partial, the event will be considered on-treatment unless there is evidence to the contrary (eg, month and year of AE start is present and is less than the month and year of the first dose of study drug). Post-treatment adverse events with onset during the follow-up period (ie, AE start date greater than the upper bound of the treatment period, as described previously) will be summarized separately.

Summaries will be presented by SOC and/or PT for all adverse events (overall and by severity), adverse events determined by the investigator to be related to study treatment (overall and by severity), serious adverse events, adverse events causing discontinuation from study treatment, and non-serious adverse events. Treatment related adverse event summaries will include events with missing relationship to study drug. For summaries by severity, patients will be counted at the greatest reported severity. Adverse events missing the flag indicating a serious adverse event will be excluded from the summary of serious adverse events, but included in the summary of non-serious adverse events.

In addition, adverse events that begin within 24 hours after study drug injection and injection-site adverse events (as recorded on the CRF) will each be summarized separately.

Summaries for the most common adverse events (incidence $\geq 2\%$ in reslizumab-treated patients) and adverse events occurring with greater frequency for reslizumab-treated patients compared to placebo will also be presented.

All adverse events, including pre-treatment events, will be included in the patient listings. The mapping of MedDRA dictionary terms for adverse event descriptions will also be provided.

7.3.1. Adverse Events of Special Interest

7.3.1.1. Administration Site Reactions

Administration site reactions will be defined based on:

- MedDRA HLT: Administration Site Reactions

Summaries will be presented by high level term (HLT), preferred term, and treatment group.

Patients will further be assessed on a 4-point Likert scale (none, mild, moderate, severe) for several domains of localized injection site tolerability including pain, tenderness, erythema, warmth, and swelling. The number and percentage of patients reported for each of the levels will be summarized descriptively for each domain by visit.

7.3.1.2. Anaphylaxis and Hypersensitivity

Anaphylaxis and hypersensitivity events will be defined based on:

- MedDRA SMQ: Anaphylactic Reaction
- MedDRA SMQ: Hypersensitivity

Summaries will be presented separately for both the broad (broad+narrow) and narrow preferred terms by treatment group.

Adverse events suspected by the investigator to be anaphylaxis events will be summarized by preferred term and treatment group. Supplemental information related to the relative timing, clinical manifestation, and treatment of these suspected events will be collected in a dedicated CRF and reported in the patient listings.

7.3.1.3. Malignancies

Malignancies will be defined based on:

- MedDRA SMQ: Malignant Tumors

Summaries will be presented by preferred term and treatment group.

7.3.1.4. Helminth infections

Helminth infections will be defined based on:

- MedDRA HLT: Ectoparasitic Disorders
- MedDRA HLT: Parasite Identification and Serology

- MedDRA HLT: Parasitic Lower Respiratory Tract Infections
- MedDRA HLT: Skin and Subcutaneous Arthropod and Parasitic Infestations

Summaries will be presented by high level term (HLT), preferred term, and treatment group.

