The immune response to parasitic infections may involve eosinophils; therefore, the clinical course of existing or new parasitic infections could potentially be complicated by a mechanism of action that lowers blood and tissue eosinophils. The iv reslizumab clinical protocols contained an exclusion criterion for patients with active or suspected helminth infestation/infection. The asthma Phase 3 studies were conducted in geographic regions in which helminth infections are prevalent, including South and Central America, Africa, and Asia. There were no helminth infections reported, and no difference was documented between the treatment groups in regards to adverse events that could be associated with gastrointestinal helminth infections.

The overall rate of infection adverse events was lower for reslizumab versus placebo-treated patients, with the types of infection events reported consistent with what would be expected in a primarily adult patient population with an underlying condition of asthma. No potential opportunistic infections were reported.

Pregnancy

The safety of reslizumab in pregnant women or developing fetus has not been studied, but nonclinical and clinical studies raised no specific concerns. As of December 2015, there have been 10 pregnancies during the entire clinical development of reslizumab, 2 of which occurred during the screening period of the study and 8 in patients receiving reslizumab. All patients were withdrawn from the study. Two pregnancies were terminated by an elective abortion with no complications, and 5 led to the birth of full-term infants with no malformations and no obstetric or perinatal complications. One male newborn had a neonatal jaundice that was reported as an unrelated adverse event and was assessed as physiological jaundice. One pregnancy case was lost to follow-up, and the outcome is unknown.

Immunogenicity

Anti-drug antibody responses were observed in 3.3% to 11.8% of patients in the completed Phase 3 studies in patients with asthma (iv administration every 4 weeks, >1000 patients evaluated for ADA). In general, the ADA responses were low in titer and often transient, and were not associated with an effect on reslizumab concentration, eosinophil count, or specific clinical manifestations (including hypersensitivity reactions).

Further details may be found in the current Investigator's Brochure.

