7.1.7.2. Protocol-Defined Adverse Events for Expedited Reporting to Teva

For the purposes of this protocol, the following are considered protocol-defined adverse events for expedited reporting to Teva: anaphylaxis, newly diagnosed malignancy, opportunistic infection, and parasitic helminth infection. Protocol-defined adverse events for expedited reporting can be either serious or nonserious according to the criteria outlined in Section 7.1.6.1. The process for reporting a protocol-defined adverse event for expedited reporting is the same as that for reporting a serious adverse event (see Section 7.1.6.3). A list of potential opportunistic infections is found in [Appendix I](#).

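### The SAP's helminth-infection search lists no MedDRA group named for helminth or gastrointestinal infection, so a coded intestinal case could be missing from that special-interest summary

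*SAP*

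**What the plan says.** SAP 7.3.1.4 opens with "Helminth infections will be defined based on" and then gives a closed list of four HLTs:

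- first, a group for ectoparasites: "MedDRA HLT: Ectoparasitic Disorders"
- second, a laboratory group: "MedDRA HLT: Parasite Identification and Serology"
- third, a lung group: "MedDRA HLT: Parasitic Lower Respiratory Tract Infections"
- fourth, a skin group: "MedDRA HLT: Skin and Subcutaneous Arthropod and Parasitic Infestations"

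Results are to be laid out by HLT and preferred term (PT) for each treatment group.

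Protocol 1.3.2.2, under Infections, gives the reason for interest: "the clinical course of existing or new parasitic infections could potentially be complicated by a mechanism of action that lowers blood and tissue eosinophils". The same passage, reporting on the earlier intravenous asthma studies, refers to "adverse events that could be associated with gastrointestinal helminth infections". Protocol 7.1.7.2 names the events that must be expedited to the sponsor: "anaphylaxis, newly diagnosed malignancy, opportunistic infection, and parasitic helminth infection". Protocol 4.2, criterion n, excludes patients with a current or recently treated helminth infection. Neither 7.1.7.2 nor criterion n restricts the infection by site.

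**The concern.** A special-interest summary exists so that a reader can take the count directly, without rebuilding it from the general listings. In a table headed helminth infections, a zero will be read as no helminth infections. If the search that feeds the table has no group for intestinal helminths, a zero would not carry that meaning.

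The question follows from the drug's mechanism, since reslizumab lowers eosinophils. The region subgroups in SAP 3.4.3 include Latin America, Asia/Pacific and Middle East/Africa. Protocol 1.3.2.2 describes South and Central America, Africa and Asia as areas where these infections are prevalent. The SAP Introduction says that the SAP prevails where it differs from the protocol, so its list would decide what the table contains.

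**Working it through.** No formula applies, and the plan gives no figure to reproduce. The check sets each listed group, read by its name, against the event the protocol describes.

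| HLT in SAP 7.3.1.4 | What the name covers | Named for helminth infection? | Named for a gastrointestinal site? |
|---|---|---|---|
| "MedDRA HLT: Ectoparasitic Disorders" | Ectoparasites | No | No |
| "MedDRA HLT: Parasite Identification and Serology" | Laboratory findings, any site | No | No |
| "MedDRA HLT: Parasitic Lower Respiratory Tract Infections" | Parasitic infection of the lower airways | No | No |
| "MedDRA HLT: Skin and Subcutaneous Arthropod and Parasitic Infestations" | Arthropods and parasites of the skin | No | No |

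The count is 0 of 4 for helminth infection and 0 of 4 for a gastrointestinal site.

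Three groups are tied to a place: the body surface, the lung, or the skin. The second is not. An event coded only as a positive parasite test could fall there whatever the organ. An event coded as a diagnosed intestinal helminth infection matches none of the four names.

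Next, whether another part of the plan fills the gap:

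1. SAP Table 10 (opportunistic infections) has no helminth term, although it does list cryptosporidiosis and isosporiasis.
2. For anaphylaxis, SAP 7.3.1.2 adds investigator-suspected events to the MedDRA search. SAP 7.3.1.4 has no such second route.
3. The SAP provides for pre-unblinding review and updating of the major-violation list (3.3.1) and the corticosteroid conversion list (6.3.2.2.3). It says nothing of the kind for this list.
4. SAP section 10 does not mention or explain a narrower helminth definition.

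Last, where such a case would still be seen:

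1. SAP 7.3: in the adverse-event tables by system organ class (SOC) and/or PT. Follow-up events are summarized separately.
2. SAP 7.3: in the patient listings, whatever the date of onset.
3. Protocol 7.1.7.2: reported by the serious-adverse-event process even if nonserious.
4. Protocol 7.8: in the periodic medical review of all adverse events.

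On scale, about 76 patients per group are planned. One omitted case would change an arm's entry from 0/76 to 1/76 = 1.3%.

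**The case against.** The strongest objection is that an HLT's content is set by the MedDRA hierarchy and not by its label. The documents give neither the hierarchy nor the version; SAP 7.3 says only that the final version will be shown in the tables. This stands. A reader might infer from the list that intestinal helminth infections will certainly go uncounted, but the documents support only that they could be missing from this summary and that the list must be checked.

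A second stronger reading is that such cases would disappear from the safety evaluation. They would not, given the other routes in SAP 7.3 and protocol 7.1.7.2 and 7.8.

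A third is that ectoparasite events would pass as helminth infections. Because results are shown by HLT and PT, each such event carries its own label, so separating or dropping those groups would add little. The risk arises only if they are added into a helminth total.

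It is also fair to say that the gastrointestinal wording in protocol 1.3.2.2 is background. It reports a negative finding from earlier studies and sets no analysis requirement here. The argument does not depend on it: 7.1.7.2 and criterion n have no site limit, so they cover the gut along with every other site.

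Finally, the practical effect is likely to be small. Active or recently treated infection is excluded at entry, and the protocol reports no helminth infections in the earlier asthma Phase 3 studies. That limits the weight of the point. It does not make the list match the event.

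**Conclusion.** The point holds in a limited form. As named, the four HLTs in SAP 7.3.1.4 do not correspond to the event that the protocol expedites and excludes, and a coded intestinal helminth infection could be absent from the helminth summary. The effect is confined to that summary. Event counts are likely to be 0 to a few, so a single omission could make the table misleading. Efficacy results, sample size, type I error and power are not affected.

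The conclusion assumes that the group names describe what the groups contain, and that a case would be coded as an infection diagnosis and not only as a test result. Confidence is therefore moderate until the list is checked against the MedDRA version in use. A correction before the tables are produced is justified because it costs so little.

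**What to change.** Add to SAP 7.3.1.4 the MedDRA grouping or groupings that cover helminth infections at all sites, including gastrointestinal. Verify the level, name and content of every listed group against the MedDRA version used for coding. Reconcile the resulting table with the events reported as parasitic helminth infection under protocol 7.1.7.2, and explain any difference.

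The ectoparasite and arthropod groups may stay, provided that they are not counted in any helminth total.

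The cost is one edit to the term list, a rerun of one table if it has already been programmed, and a short medical review of the wider list.

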7.3.1.5. Muscle Disorders

Muscle disorders will be defined based on:

- MedDRA HLGT: Muscle Disorder
- MedDRA PT: Blood Creatine Phosphokinase Increased

Summaries will be presented by high level term (HLT), preferred term, and treatment group.

7.3.1.6. Opportunistic Infections

Opportunistic infections will be defined based on the following list of terms, derived from the preferred term (PT) or low level term (LLT) summarized in [Table 10](#). The FDA terms provided are from the Panel on Opportunistic Infections in HIV-Infected Adults and Adolescents.

Summaries will be presented by preferred term and treatment group.

Table 10: List of Search Terms for Opportunistic Infections

Term	Code	Level	FDA term (if applicable)	If LLT- under which PT
Acinetobacter infection	10051894	PT	Acinetobacter infection	
Aspergillus infection	10074171	PT	Aspergillosis	
Blastomycosis	10005098	PT	Blastomycosis, extrapulmonary	
Burkitt's lymphoma	10006595	PT	Burkitt's lymphoma	
Oesophageal candidiasis	10030154	PT	Candidiasis of esophagus	
Cerebral toxoplasmosis	10057854	PT	Toxoplasmosis of brain	
Cervix carcinoma	10008342	PT	Cervical cancer invasive	
Coccidioidomycosis	10009825	PT	Coccidioidomycosis, disseminated or extrapulmonary	
Cryptococcosis	10011490	PT	Cryptococcosis, extrapulmonary	
Cryptosporidiosis infection	10011502	PT	Cryptosporidiosis infection, chronic intestinal (> 1 month duration)	
Cytomegalovirus chorioretinitis	10048843	PT	Cytomegalovirus disease (other than liver, spleen, or nodes)	
Cytomegalovirus colitis	10048983	PT	Cytomegalovirus disease (other than liver, spleen, or nodes)	

Term	Code	Level	FDA term (if applicable)	If LLT- under which PT
Cytomegalovirus duodenitis	10049014	PT	Cytomegalovirus disease (other than liver, spleen, or nodes)	
Cytomegalovirus enteritis	10049074	PT	Cytomegalovirus disease (other than liver, spleen, or nodes)	
Cytomegalovirus enterocolitis	10049015	PT	Cytomegalovirus disease (other than liver, spleen, or nodes)	
Cytomegalovirus gastritis	10049016	PT	Cytomegalovirus disease (other than liver, spleen, or nodes)	
Cytomegalovirus gastroenteritis	10051349	PT	Cytomegalovirus disease (other than liver, spleen, or nodes)	
Cytomegalovirus gastrointestinal infection	10052817	PT	Cytomegalovirus disease (other than liver, spleen, or nodes)	
Cytomegalovirus infection	10011831	PT	Cytomegalovirus disease (other than liver, spleen, or nodes)	
Cytomegalovirus mononucleosis	10011834	PT	Cytomegalovirus disease (other than liver, spleen, or nodes)	
Cytomegalovirus mucocutaneous ulcer	10065036	PT	Cytomegalovirus disease (other than liver, spleen, or nodes)	
Cytomegalovirus myelomeningoradiculitis	10065621	PT	Cytomegalovirus disease (other than liver, spleen, or nodes)	
Cytomegalovirus myocarditis	10056261	PT	Cytomegalovirus disease (other than liver, spleen, or nodes)	
Cytomegalovirus oesophagitis	10049018	PT	Cytomegalovirus disease (other than liver, spleen, or nodes)	
Cytomegalovirus pancreatitis	10049566	PT	Cytomegalovirus disease (other than liver, spleen, or nodes)	
Cytomegalovirus pericarditis	10056721	PT	Cytomegalovirus disease (other than liver, spleen, or nodes)	
Cytomegalovirus syndrome	10056262	PT	Cytomegalovirus disease (other than liver, spleen, or nodes)	
Cytomegalovirus urinary tract infection	10051350	PT	Cytomegalovirus disease (other than liver, spleen, or nodes)	
Cytomegalovirus viraemia	10058854	PT	Cytomegalovirus disease (other than liver, spleen, or nodes)	
Disseminated cytomegaloviral infection	10049075	PT	Cytomegalovirus disease (other than liver, spleen, or nodes)	

Term	Code	Level	FDA term (if applicable)	If LLT- under which PT
Encephalitis cytomegalovirus	10014586	PT	Cytomegalovirus disease (other than liver, spleen, or nodes)	
Pneumonia cytomegaloviral	10035676	PT	Cytomegalovirus disease (other than liver, spleen, or nodes)	
Hepatitis B	10019731	PT	Hepatitis B	
Hepatitis C	10019744	PT	Hepatitis C	
Herpes simplex skin chronic ulcers	10058426	LLT	Herpes simplex ulcers chronic (>1mo)	Under "Herpes dermatitis" PT
Herpes simplex	10019948	PT	Herpes simplex bronchitis	
Herpes simplex pneumonia	10065046	PT	Herpes simplex pneumonitis	
Herpes simplex oesophagitis	10074242	PT	Herpes simplex oesophagitis	
Shingles	10040555	LLT	Shingles when 2 distinct episodes or more than 1 dermatome	Under "Herpes zoster" PT
Histoplasmosis	10020141	PT	Histoplasmosis extrapulmonary	
Histoplasmosis disseminated	10020144	PT	Histoplasmosis disseminated	
HIV wasting syndrome	10050309	PT	Wasting secondary to HIV	
Human polyomavirus infection	10057366	PT	Human polyomavirus infection	
Immunoblastic lymphoma	10053574	PT	Lymphoma immunoblastic	
Isosporiasis	10023076	PT	Isosporiasis, chronic intestinal (> 1 month's duration)	
Kaposi's sarcoma	10023284	PT	Kaposi's sarcoma	
Lymphoid interstitial pneumonia	10062997	LLT	Lymphoid interstitial pneumonia	Under "Interstitial lung disease" PT
Listeriosis	10024641	PT	Listeriosis	
Mycobacterial infection	10062207	PT	Mycobacterium infections, other species or unidentified species, disseminated or extrapulmonary (eg, M. haemophilium, M. fortuitum, or M. marinum)	
Mycobacterium avium complex infection	10058806	PT	Mycobacterium avium complex disseminated or extrapulmonary	
Mycobacterium kansasii infection	10028447	PT	M. Kansasii, disseminated or extrapulmonary	

Term	Code	Level	FDA term (if applicable)	If LLT- under which PT
Nocardiosis	10029444	PT	Nocardiosis	
Pneumocystis jirovecii infection	10073756	PT	Pneumocystis jirovecii infection	
Pneumonia recurrent	10066727	LLT	Pneumonia recurrent	Under "Pneumonia" PT
Polyomavirus-associated nephropathy	10065381	PT	Polyomavirus (JC virus or BK virus)-associated nephropathy (including progressive multifocal leukoencephalopathy)	
Primary central nervous system lymphoma	10036685	LLT	Lymphoma primary of brain	
Candidiasis of bronchi	10064443	LLT	Candidiasis of bronchi	Under "Respiratory moniliasis" PT
Candidiasis of trachea	10064459	LLT	Candidiasis of trachea	Under "Respiratory moniliasis" PT
Candidiasis of lung	10007155	LLT	Candidiasis of lungs	Under "Respiratory moniliasis" PT
Salmonella sepsis	10058878	PT	Salmonella sepsis	
Salmonella septicemia	10039445	LLT	Salmonella septicemia, recurrent	Under "Salmonella sepsis" PT
Salmonella sepsis recurrent	10066745	LLT	Salmonella sepsis if recurrent	Under "Salmonella sepsis" PT
Active tuberculosis	10071157	LLT	Any active TB	Under "Tuberculosis" PT
Mycobacterium tuberculosis NOS	10028461	LLT	Mycobacterium tuberculosis, any site, latent or active	Under "Tuberculosis" PT

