APPENDIX I. OPPORTUNISTIC INFECTIONS

Potential opportunistic infections include, but are not limited to, the following:

- Acinetobacter infection
- Aspergillosis
- Blastomycosis, extrapulmonary
- Burkitt's lymphoma
- Candidiasis of esophagus, bronchi, trachea, or lungs
- Cervical cancer invasive
- Coccidioidomycosis, disseminated or extrapulmonary
- Cryptococcosis, extrapulmonary
- Cryptosporidiosis infection, chronic intestinal (>1 month duration)
- Cytomegalovirus disease (other than liver, spleen, or nodes)
- Hepatitis B and C
- Herpes simplex bronchitis, pneumonitis, or esophagitis
- Herpes simplex ulcers chronic (>1 month)
- Herpes zoster (Shingles) when 2 distinct episodes or more than 1 dermatome
- Histoplasmosis disseminated or extrapulmonary
- Human polyomavirus infection
- Isosporiasis, chronic intestinal (>1 month's duration)
- Kaposi's sarcoma
- Listeriosis
- Lymphoid interstitial pneumonia
- Lymphoma immunoblastic
- Lymphoma primary of brain
- Mycobacterium avium complex or *M. kansasii*, disseminated or extrapulmonary Mycobacterium infections, other species or unidentified species, disseminated or extrapulmonary (eg, *M. haemophilium*, *M. fortuitum*, or *M. marinum*)
- Mycobacterium tuberculosis, any site, latent or active
- Nocardiosis
- Pneumocystis jiroveci infection
- Pneumonia, recurrent

- Polyomavirus (JC virus or BK virus)-associated nephropathy (including progressive multifocal leukoencephalopathy)
- Salmonella sepsis
- Salmonella septicemia, recurrent
- Shingles
- Toxoplasmosis of brain
- Any active tuberculosis
- Wasting secondary to human immunodeficiency virus (HIV)

Source: Modified from the Panel on Opportunistic Infections in HIV-Infected Adults and Adolescents. Guidelines for the prevention and treatment of opportunistic infections in HIV-infected adults and adolescents: recommendations from the Centers for Disease Control and Prevention, the National Institutes of Health, and the HIV Medicine Association of the Infectious Disease Society of America. Available at http://aidsinfo.nih.gov/contentfiles/lvguidelines/adult_oi.pdf.

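### SAP Table 10 searches zoster and tuberculosis only through selected low-level terms and names no term for PML, so the opportunistic-infection summary may depend on how the reporter worded the event

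*SAP*

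**What the plan says.** SAP 7.3.1.6 makes the list the definition: "Opportunistic infections will be defined based on the following list of terms". Each row of Table 10 gives a search term, its level (PT or LLT), the corresponding FDA term where there is one and, for most LLT rows, the parent PT. The display rule is "Summaries will be presented by preferred term and treatment group".

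The rows that matter here are:

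- **Zoster.** One row, the LLT *Shingles*, with Herpes zoster as parent. Its FDA-term cell reads "Shingles when 2 distinct episodes or more than 1 dermatome".
- **Tuberculosis.** Two rows, the LLTs *Active tuberculosis* and *Mycobacterium tuberculosis NOS*, both with Tuberculosis as parent. The second is mapped to the FDA term for tuberculosis at any site, latent or active.
- **PML.** No row of its own. It appears only in the FDA-term cell of the PT *Polyomavirus-associated nephropathy*: "Polyomavirus (JC virus or BK virus)-associated nephropathy (including progressive multifocal leukoencephalopathy". A second polyomavirus row, the PT *Human polyomavirus infection*, does not mention PML.

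Protocol Appendix I, the list to which the protocol refers investigators, names herpes zoster (with shingles in brackets) under the episode/dermatome qualifier. It then lists shingles again without any qualifier. For tuberculosis it has "Mycobacterium tuberculosis, any site, latent or active" and a separate entry for any active tuberculosis. It names PML within the nephropathy entry.

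**The concern.** If an LLT row retrieves only events coded to that LLT, a patient whose event was written down as shingles enters the special-interest table, while a patient with the same illness coded through a different LLT of Herpes zoster does not. The same applies to tuberculosis. Counts in this table will be very small, so one case gained or lost through wording can change how the arms compare.

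The LLT does not deliver the intended restriction either. The term *Shingles* carries no information on number of episodes or dermatomes. A single-dermatome case reported as shingles would be counted, and a multi-dermatome case coded elsewhere under Herpes zoster would not.

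There is also a presentational problem. Because the summary is shown by PT, the retrieved cases would appear under Herpes zoster, and that row could disagree with the Herpes zoster row in the general adverse-event table without explanation.

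The missing PML term and the weak latent tuberculosis term are a separate defect. They concern which terms are on the list, not the level at which they match.

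**Working it through.** The plan gives no figure to reproduce, so the check is a comparison of lists, followed by a rough size.

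**1. Composition of Table 10.** Counted by hand, there are 64 rows: 52 PT and 12 LLT. Eleven of the 12 LLT rows name a parent; *Primary central nervous system lymphoma* does not. Seven distinct parents are named: Herpes dermatitis, Herpes zoster, Interstitial lung disease, Pneumonia, Respiratory moniliasis, Salmonella sepsis and Tuberculosis. Only Salmonella sepsis is also a search row.

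**2. Which matching level is meant?** SAP 7.3.1.6 does not say. Three features favour LLT matching:

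- The table has a column for the level of each term.
- Salmonella sepsis is listed as a PT, and two LLTs beneath it are listed as well. If an LLT row selected its whole parent, those rows would add nothing.
- *Pneumonia recurrent* sits under Pneumonia. Parent matching would turn every pneumonia into an opportunistic infection.

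**3. What each reading does.**

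| Event coded to | LLT matching | Parent-PT matching |
|---|---|---|
| LLT *Shingles* | counted | counted |
| another LLT of Herpes zoster | missed | counted |
| LLT *Active tuberculosis* or *Mycobacterium tuberculosis NOS* | counted | counted |
| another LLT of Tuberculosis | missed | counted |
| any pneumonia not coded as recurrent | not counted | counted |

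The first reading under-counts zoster and tuberculosis. The second over-counts pneumonia. The table itself shows that a PT can hold several LLTs (three under Respiratory moniliasis, two each under Salmonella sepsis and Tuberculosis). That Herpes zoster and Tuberculosis hold LLTs beyond those listed is an assumption, to be confirmed in the coding dictionary.

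**4. Table 10 against Appendix I.**

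| Appendix I | Table 10 search term |
|---|---|
| Herpes zoster, qualified | LLT *Shingles* only |
| Shingles, unqualified | same LLT; the FDA-term cell carries only the qualified version |
| Tuberculosis, latent or active | LLT *Mycobacterium tuberculosis NOS*; no term names latent disease |
| Any active tuberculosis | LLT *Active tuberculosis* |
| PML, within the nephropathy entry | PT *Polyomavirus-associated nephropathy*; no term names PML |

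**5. Rough size for zoster.** Inputs: 152 planned patients (protocol 9.1, 76 per group) and 24 weeks of treatment; no dropout is assumed. The zoster rate is not in the documents and is assumed to be 1 to 3 per 100 patient-years.

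- Exposure: 152 × 24 / 52 = 70.2 patient-years.
- Expected zoster of any kind, both arms: 70.2 × 0.01 = 0.7 to 70.2 × 0.03 = 2.1.
- Per arm: 0.35 to 1.05.
- Expected loss: (1 − f) × (0.7 to 2.1), where f is the share coded to *Shingles*. With f = 0.5, as an illustration, this is 0.35 to 1.05 cases over both arms. It falls to zero as f approaches 1.

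These are all zoster cases. Cases meeting the two-episode or multi-dermatome qualifier would be fewer. The documents give no basis for a tuberculosis or PML rate.

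**The case against.** The strongest objection is that the omission has not been demonstrated. The SAP never says that matching stops at the LLT, the table names each parent, and the output is by PT, so a programmer might select the parent. This stands to the extent that the matching level is inferred. It does not rescue the plan, because the parent reading would sweep in all pneumonia, and an unstated rule is itself something to settle before unblinding.

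A reader might infer that latent tuberculosis has been left out of the search. The documents do not support that: *Mycobacterium tuberculosis NOS* is mapped to an entry that includes latent disease. What remains is that an unspecified term under Tuberculosis may not retrieve an event coded as latent.

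On PML, Table 10 copies the structure of Appendix I, which also mentions it only inside the nephropathy entry, and *Human polyomavirus infection* is searched too. Both points are fair. Neither gives a search term that names PML, and whether the dictionary version used has a separate one cannot be checked from the documents.

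Finally, the consequence is limited. Under SAP 7.3 all on-treatment events are summarised by system organ class and/or PT, serious events and those causing discontinuation are summarised separately, all events are listed, and the dictionary mapping is provided. Protocol 7.1.7.2 bases expedited reporting on the investigator's report with Appendix I as a guide, and that list is open-ended. This objection stands in full.

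**Conclusion.** The point holds as a gap in one descriptive safety table. Under the reading that the table's structure favours, zoster and tuberculosis events that Appendix I intends to cover could be absent from the opportunistic-infection summary according to the reporter's wording. Separately, PML has no search term of its own and latent tuberculosis relies on an NOS term.

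For zoster, about 0.7 to 2.1 cases of any kind are expected across both arms, and the loss is only the part not coded to *Shingles*. This rests on the assumed rate, on no dropout, on LLT-level matching, and on the two PTs having LLTs that Table 10 does not list.

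A reader might go further and infer that such events would vanish from the safety evaluation, or that expedited reporting would miss them. The documents do not support either: the general tables and listings retain the events, and expedited reporting does not use Table 10. The primary analysis, type I error control and power are untouched.

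**What to change.** Amend Table 10 before unblinding:

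1. Replace the zoster and tuberculosis LLT rows with the PTs Herpes zoster and Tuberculosis.
2. Add explicit search terms for PML and latent tuberculosis, after checking what the MedDRA version used for coding provides.
3. State in 7.3.1.6 that the remaining LLT rows match at LLT level, so that *Pneumonia recurrent*, for example, does not bring in all pneumonia.
4. Have a blinded medical reviewer flag the zoster cases with two distinct episodes or more than one dermatome, since a coded term cannot show this. Because Appendix I lists shingles both with and without that limit, present all zoster with the flagged subset marked.

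The cost is a few lines in the table and a short blinded review of what should be a handful of cases. The downside is that single-dermatome zoster enters the summary and must be distinguished by the flag.
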